Investigators and Trial Centres: The overall design and conduct of this investigator-initiated study will be the responsibility of the Steering Committee. This a collaborative trial designed and coordinated jointly by independent investigators at the National Institute of Health Innovation (University of Auckland), the Dept. of General Practice and Primary Care (University of Auckland), and Auckland District Health Board, with input from clinicians at Auckland DHB, Counties Manukau DHB, Waikato DHB, the Nurse Maude Association Christchurch, and the Southern DHB. Publication of data from this trial will be the responsibility of the Steering Committee. The trial will be co-ordinated from the NIHI, with participants recruited from patients attending the district nursing services at Auckland DHB, Counties Manukau DHB, Waikato DHB, the Nurse Maude Association Christchurch, and the Southern DHB.

Trial Period: Oct 2014 – Oct 2017

Clinical Phase: Phase III

Objectives: The objective of this trial is to determine the effectiveness of low dose aspirin compared to placebo when used in addition to compression therapy for venous leg ulcer healing.

Duration of Treatment: The maximum duration of treatment is 24 weeks (or less if the ulcer heals within 24 weeks).

Trial Design and Methodology

A prospective community-based, double-blind, placebo-controlled, randomised trial with participants receiving either 150 mg aspirin daily for up to 24 weeks or matching placebo. Block randomisation will be used, stratified by trial centre and prognostic index (ulcer size and duration) to ensure a balance of participants within trial centres and for participants likely to be slow healers. Participants in both arms will also receive compression therapy (with system of choice guided by patient and/or clinical preference) as delivered through district nursing services at the trial centres. Assessment of health-related quality of life will be carried out at baseline and at the end of the trial treatment period. The patient will continue to receive district nursing care as per normal protocol.

Inclusion/exclusion criteria: Patients with leg ulcers will be eligible for *inclusion* if they meet the following criteria:

- Aged 18 years or older
- Determined to have a venous leg ulcer (clinical indications of venous ulceration, ABI \geq 0.8, and other causative aetiologies ruled out)
- Able to tolerate compression therapy
- Able to provide written informed consent
- Confirmation with participant's general practitioner that the participant can take low dose aspirin or placebo.

Potentially eligible participants will be *excluded* if they meet any of the criteria below:

- Pregnant or breast-feeding women
- History of myocardial infarction, stroke, transient ischaemic attack, angina or significant peripheral arterial disease
- History of adverse effects related to aspirin use

- Currently using aspirin, or other anti-platelet or anticoagulant therapy
- Participant has any other existing condition or treatment that is a contraindication to use of aspirin or to participation in the trial
- Participant has any other existing condition where treatment with aspirin is indicated.

Test Product:

- Aspirin 150 mg daily + compression bandaging

Reference Therapy:

- Placebo daily + compression bandaging

Primary Outcome:

Time to complete healing over 24 weeks. Complete healing is defined as full epithelialisation of the ulcer with no scab.

Secondary outcomes:

- Proportion with healed reference VLU at 24 weeks
- Change in estimated reference ulcer area from baseline to 24 weeks
- Adherence with aspirin
- Change in health-related quality of life from baseline to 24 weeks
- Adverse events
- Efficacy of blinding.

Sample size: A sample size of 354 (177 in each group) will be sufficient to show a **four week** difference in time-to-healing at 90% power with an alpha of 0.05, assuming the median time-to-healing in the control group over a six month follow up is 92 days and allowing for 10% loss to follow up.

Statistical analysis: All analyses will use intention-to-treat in accord with a Statistical Analysis Plan developed *a priori*. Time-to-event data will be analysed using Kaplan Meier plots, log rank test and Cox regression. Simple incidence rates, relative risks and 95% CIs will be obtained for all binary variables in the first instance, with multiple logistic regression analysis if necessary to adjust for imbalance. Continuous outcomes will be analysed using multiple linear regression and adjusted for baseline value and other covariates if needed. A *kappa* will be calculated for the evaluation of the efficacy of blinding.

2. Background

2.1 Prevalence of leg ulceration

Leg ulceration is a chronic, relapsing and remitting condition. Recurrence within five years is 30-70%.^{1,2} Period prevalence for leg ulceration is 1.13/1000 New Zealand adults per year and increases with age (80+ years 13/1000).³ New Zealand has a rapidly ageing population with the proportion of older people expected to increase from 12% to 25% of the population by 2020-2030.⁴ Thus the number of people with leg ulcers can be expected to double from a current estimate of 5506 per year in 2011 to 9781 per year in 2031 (*Statistics New Zealand* population projections series 5). Venous leg ulcers comprise the majority (up to 84%) of all leg ulcers.^{5,6}

2.2 Economic Implications of Leg Ulceration

Leg ulcers represent a significant cost to community services as they are slow to heal and the majority of patients require nursing care at least once per week plus general practitioner consultations. It has been estimated that district nurses in Auckland spend approximately 25% of their time on venous ulcer management.⁷ An audit of a New Zealand district nursing service in 1999 found the average cost of treatment with compression was \$906 for a first time ulcer and \$1205 for a recurrent ulcer (pers. comm. [name]). The actual cost ranged from \$156 to \$5626 depending on time to healing. The average cost of an unhealed ulcer at 12 weeks was found to be \$1405 compared to \$535 for those that healed by 12 weeks in a New Zealand clinical trial.⁸

2.3 Effects of Leg Ulceration on Health

Leg ulceration is reported as having an impact on virtually every aspect of daily life and is associated with feelings of powerlessness, loss of control, and states of hopelessness.⁹⁻¹³ Pain, sleep impairment, and reduced mobility are commonly reported,^{10,12,14-17} work capacity can be restricted and personal finances adversely affected.^{9,18} Social activities may be avoided in order to reduce the risk of injury to legs,¹⁹ or minimized due to negative body image, with loneliness a frequent consequence.^{11,14,20} In New Zealand, leg ulceration has been shown to have a significant adverse impact on health-related quality of life as measured by the SF 36-Item Health survey; RAND-36 is a version of SF-36.²¹ Ulcer healing improves quality of life as measured by a disease-specific tool in a New Zealand trial,²² and earlier healing will increase patients' quality of life, especially in the older people who more commonly have leg ulcers.

2.4 Treatments for Venous Ulceration

The therapeutic mainstay in management of venous ulceration is graduated compression bandaging (changed once weekly) or stockings (removed daily). No single system of compression is more effective than other systems, although multi-component systems are superior to single component systems and systems that contain an elastic layer are better than those with inelastic components.²³ However, 30-60% of patients still remain unhealed after 12 weeks of treatment with compression therapy.²⁴⁻²⁷ In a New Zealand trial (n=368), the proportion of participants with unhealed venous leg ulcers after 12 weeks treatment with compression bandaging was 50%.⁸

Compression bandaging should only be applied in the absence of significant arterial disease. The threshold normally employed for the use of compression is an ankle brachial pressure (ABI) index of 0.8.²⁸ An ABI is the ratio of the systolic blood pressure at the arm over the systolic blood pressure at the ankle. A normal adult value for the ABI is between 0.9 and 1.2. Levels lower than 0.8 are thought

to indicate the presence of moderate arterial disease, although selected patients with an ABI of between 0.6-0.8 can safely receive reduced levels of compression bandaging.¹⁸

The only available adjuvant to compression in New Zealand is oxpentifylline (also known as pentoxifylline or Trental), which increases healing rates by 60% (Relative Risk 1.56, 95%CI 1.14 – 2.13),²⁹ but there are real barriers to its routine use: [1] pentoxifylline is not registered in New Zealand for routine management of venous leg ulcers; [2] while prescribing no longer requires special authorisation, having previously done so means general practitioners are perhaps not familiar with the drug; [3] the drug is only partially subsidized (co-payment of ~\$20.00 per month); and [4] the drug must be taken three times per day increasing polypharmacy in the elderly. Effective affordable additional treatments for venous leg ulceration are needed, ideally incurring little extra cost to health services or patients. One promising adjuvant treatment for venous leg ulceration is oral aspirin.

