2.5 Aspirin as a potential treatment

Two randomised trials of oral aspirin in addition to compression have been reported.^{30,31} Combined into a meta-analysis (figure 1), the pooled healing rate favoured 300 mg aspirin at 16 weeks (RR 1.62, 95%CI 0.99 – 2.65). However, there are methodological issues with these trials. Both trials excluded patients commonly seen in clinical care who would be treated with compression – those with small ulcers or those with slightly reduced blood flow to the lower leg (ankle brachial index 0.8 to 0.9). Further, the trial regimens likely excluded many of the very old (who have increased incidence of VLU) as the average ages in the trials were 64.1 years and 59.5 years. Most importantly, the trials were too small to provide the substantive evidence needed to change current practice.

[figure not shown]

Figure 1. Meta-analysis of two trials of comparing aspirin plus compression to placebo plus compression

Platelet inhibition by aspirin is achieved by doses lower than 300 mg. However, variability in response to low-dose aspirin, independent of compliance, has been described. Aspirin formulation, obesity, and rate of platelet turnover are all associated with low response.³² While a 150 mg dose is at the higher end of the low-dose range,³³ it offers a responsible compromise dose that allows for variability in response to low-dose aspirin as well as increased risk with the very old. A secondary analysis of data from the HALT trial (led by the applicant, n=368)⁸ found 150mg aspirin was associated with the strongest effect on VLU healing rates, (adjusted for baseline ulcer size and duration, Hazard Ratio 1.77, 95%CI 1.13–2.75).

Anecdotally, the main barrier to further testing of aspirin for VLU healing has been the view that it would be difficult to recruit VLU patients, as many would be older adults thought to already be taking aspirin for other indications. However, two New Zealand VLU trials showed aspirin use was only 30% of participants in one (recruitment 2003-2005) and 17% in the second (recruitment 2007).⁸ The low use of aspirin was not explained by contraindications. These findings are similar to the 34% of VLU patients taking aspirin in a 2010 audit of 50 VLU patients in Christchurch (pers.comm., [name]).

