6.2 Case definition

Only patients with venous leg ulcers being treated through the trial centres will be recruited. A patient will be considered to have a purely venous leg ulcer where other causative aetiologies (diabetes, rheumatoid arthritis, malignancy) have been ruled out, the ulcer appears clinically venous (presentation may include any or all of the following: moist, shallow, irregular shape; haemosiderian pigmentation; venous eczema; ankle oedema; ankle flare; lipodermatosclerosis), and the trial participant has an Ankle Brachial Index (ABI) ≥ 0.8 to rule out arterial insufficiency. For the purposes of this trial, an incident leg ulcer will be considered to be any break in the skin on the leg (below the knee) that has been present for four or more weeks. If a patient known to a service presents with a new episode of ulceration, has a prior history of venous leg ulceration, is considered to have a

current venous leg ulcer, they will be candidates for participation. Patients with prevalent ulcers meeting the case definition already in treatment will also be eligible for inclusion.

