6.3 Eligibility criteria

Patients with leg ulcers will be eligible for *inclusion* if they meet the following criteria:

- Aged 18 years or older
- Determined to have a venous leg ulcer (clinical indications of venous ulceration, ABI \geq 0.8, and other causative aetiologies ruled out)
- Able to tolerate compression therapy
- Able to provide written informed consent
- Confirmation with participant's general practitioner that the participant can take low dose aspirin or placebo.

Potentially eligible participants will be *excluded* if they meet any of the criteria below:

- Pregnant or breast-feeding women
- History of myocardial infarction, stroke, transient ischaemic attack, angina or significant peripheral arterial disease
- History of adverse effects related to aspirin use
- Currently using aspirin, or other anti-platelet or anticoagulant therapy
- Participant has any other existing condition or treatment that is a contraindication to use of aspirin or to participation in the trial
- Participant has any other existing condition where treatment with aspirin is indicated.

7. Randomisation and allocation concealment

On registration (week -1) participants will be assigned a unique sequential registration number using numbers generated by the NIHI data management. When a registration number has been allocated, the participant's initials and date of birth and the date of registration must be recorded. This registration number will be used to identify the participant throughout all periods of the trial. Once a registration number has been assigned, it may not be used again.

Immediately after baseline data have been recorded, consented patients who fulfil entry criteria will be randomised by computer to one of the two trial groups using stratified blocked randomisation with varying block sizes of 2 and 4. The randomisation sequence will be prepared by the trial statistician and loaded into a secure database. Randomisation will be stratified by trial centre and prognostic index (based on ulcer and duration) which will isolate any centre effect in clinical management and ensure a balance on key prognostic variables known to influence healing at 24 weeks. Each treatment pack is uniquely numbered and is allocated using the randomisation sequence. The Research Nurse accesses the randomisation web-page, completes data entry, and generates the allocation using a computerised tablet. The allocated treatment is then given to the participant by the Research Nurse.

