10.1 Baseline assessments

Screening information will be obtained from a telephone contact with the patient at week -1. Eligible patients will be visited at Week -1 and, once consented, the following baseline data will be collected immediately prior to randomisation:

- Demography: age, sex, self-reported ethnicity.
- Ulcer area and duration: Reference VLU area (area > 5 cm²) and duration (duration for > six months) provide data for a prognostic index for VLU healing with 24 weeks of compression.⁵⁸ The index assigns scores of 0, 1 or 2 based on absence of both factors, presence of one factor, or presence of both factors. Sophisticated tools for measuring ulcer area are either too expensive (e.g. SilhouetteTM) or no longer supported by the manufacturer in New Zealand (e.g. VisitrakTM). A simpler method of estimation using the formula for area of an ellipse has been shown to be highly correlated with ulcer area, both in the literature ($r = 0.951$)⁵⁰ and internal data from one of our previous trials ($r = 0.92$).⁸ Ulcer duration will be obtained from patient recall. Where more than one VLU is present, the largest ulcer will be the reference ulcer.
- ABI: An ABI < 0.8 indicates that there is a high probability that some arterial insufficiency is present (positive predictive value = 95% in a general practice population).⁵⁹ Use of compression therapy where significant arterial disease is present can result in severe ischaemia in the leg,

with risk of necrosis. Consequently ABIs are routinely obtained for all patients with incident ulcers under the care of each of the trial centres taking part in the proposed trial, to confirm suitability for compression therapy. An ABI will be obtained from the clinical records for each participant. Where a potential participant already in treatment has an ABI obtained more than three months prior to the eligibility screen, a new ABI will be obtained prior to inclusion to ensure no development or progression of arterial disease.

- Clinical history and concomitant medications.
- Compression system: Details of the patient’s current treatment regime will be recorded.
- Health-related quality of life (HRQoL) instruments: The RAND 36-item Health Survey⁵¹, EQ5D,⁵⁴ and the Charing Cross Venous Ulcer Questionnaire (CXVUQ)⁵² will be administered.

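### Does the inverted definition of the ankle brachial index in section 2.4 undermine the ABI ≥ 0.8 inclusion rule?

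*Protocol*

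**What the plan says.** Section 2.4 of the Protocol introduces the index in a background paragraph on compression: "An ABI is the ratio of the systolic blood pressure at the arm over the systolic blood pressure at the ankle". The paragraph goes on: "A normal adult value for the ABI is between 0.9 and 1.2". It then says of low values: "Levels lower than 0.8 are thought" "to indicate the presence of moderate arterial disease".

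The other sections use the index as follows.

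- Section 2.5, on patients left out of previous aspirin trials: "slightly reduced blood flow to the lower leg (ankle brachial index 0.8 to 0.9".
- Section 6.2, in the case definition: "Ankle Brachial Index (ABI) ≥ 0.8 to rule out arterial insufficiency".
- Section 6.3, as an inclusion criterion with the same cut-off: "Determined to have a venous leg ulcer (clinical indications of venous ulceration, ABI" of at least 0.8.
- Section 10.1, which treats a value below 0.8 as making arterial insufficiency highly probable. It takes the ABI from the clinical record. For a patient already in treatment whose value is more than three months old, "a new ABI will be obtained prior to inclusion to ensure no development or progression of arterial disease".

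Sections 10.2 and 10.3 list recording or obtaining the ABI as a Visit 1 task. None of sections 6.2, 6.3, 10.1, 10.2 or 10.3 restates the ratio or points back to section 2.4.

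**The concern.** If arm pressure is divided by ankle pressure, the index rises as ankle pressure falls. A cut-off that admits values of 0.8 and above would then let through the legs it is meant to keep out.

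The cut-off is an inclusion criterion, and section 2.4 holds the only definition in the text available for review. Someone looking up how to calculate the index would find only this sentence. Section 10.1 warns that compressing a leg with serious arterial disease can lead to ischaemia and tissue death. The exclusion for a history of significant peripheral arterial disease catches known disease only. If staff did calculate from the sentence, patients with undiagnosed arterial disease could be enrolled as having purely venous ulcers.

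**Working it through.** **Inputs.** The written ratio is w = arm / ankle (section 2.4). Let r = ankle / arm, so w = 1/r. The cut-off is 0.8 (sections 2.4, 6.2, 6.3, 10.1). The normal band is 0.9 to 1.2 (section 2.4). An arm pressure of 140 mmHg is assumed for illustration; it cancels out of the ratio and does not affect the result.

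**1. The rule taken literally.** w ≥ 0.8 is the same as r ≤ 1/0.8 = 1.25.

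| Ankle (mmHg) | r = ankle/arm | w = arm/ankle | w ≥ 0.8? | r ≥ 0.8? |
|---|---|---|---|---|
| 56 | 0.40 | 2.50 | yes | no |
| 84 | 0.60 | 1.67 | yes | no |
| 98 | 0.70 | 1.43 | yes | no |
| 112 | 0.80 | 1.25 | yes | yes |
| 140 | 1.00 | 1.00 | yes | yes |
| 168 | 1.20 | 0.83 | yes | yes |
| 182 | 1.30 | 0.77 | no | yes |

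The literal rule excludes no leg with ankle pressure below arm pressure.

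**2. Does it also turn away healthy legs?** If the normal band of 0.9 to 1.2 is on the ankle/arm scale, it becomes 1/1.2 = 0.83 to 1/0.9 = 1.11 on the written scale. All of it is above 0.8, so every leg in the band passes on either reading. The literal rule rejects only r > 1.25, which is outside the protocol's own normal band. Nothing in the document says that such legs are free of arterial disease, so this half of the concern is not supported.

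**3. Can the written ratio be squared with the other passages?**

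- Section 2.5 calls 0.8 to 0.9 slightly reduced flow. On the written ratio this is r from 1/0.9 = 1.11 to 1/0.8 = 1.25, that is, ankle pressure 11% to 25% above arm pressure. That is not reduced flow.
- Section 2.4 says selected patients at 0.6 to 0.8 can have reduced compression. On the written ratio this is r from 1/0.8 = 1.25 to 1/0.6 = 1.67, which would mean cautious compression for the legs with the highest ankle pressures.
- Sections 6.2 and 10.1 make 0.8 the line below which arterial insufficiency is suspected. On the written ratio the legs below that line are those with r > 1.25.

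Each use makes sense only if the index falls as ankle pressure falls. One sentence is out of step with the rest, including the lines that follow it in its own paragraph.

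**4. Where the trial's values come from.** Section 10.1 says the participating services obtain ABIs routinely for incident ulcers, to confirm that compression is suitable, and that the trial reads the value from those records. The repeat measurement applies only to patients already in treatment with an old value. Section 6.1 says the centres took part in previous leg ulcer trials. Section 11.1 cites 212 new Doppler assessments in one year at one centre. No step asks anyone to calculate the index from section 2.4.

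**The case for a change.** The best argument for acting is that the sentence is wrong by the protocol's own lights, bears on a safety-relevant inclusion criterion and would cost one line to correct. The stated normal range would not readily alert a reader, because 0.9 to 1.2 inverts to 0.83 to 1.11, which largely overlaps it. The error shows only at the diseased end, where the criterion has to work. The Appendix 4 amendments shown do not list a correction.

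The contradiction and the arithmetic stand. It does not follow that the sentence governs enrolment. To admit a diseased leg because of it, a nurse would have to set aside routine practice, the name of the index, and the statements in sections 2.4, 6.2 and 10.1 about what a low value means. The ischaemia argument also weakens on inspection. Compression is not the randomised treatment: both arms receive it through the district nursing services (section 4), and those services' own ABI decides whether it is suitable. A sentence in the trial background does not alter how they measure it.

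Other criteria also narrow the route in: a clinically venous ulcer with other causes ruled out, tolerance of compression, and no history of significant peripheral arterial disease. They do not replace the ABI, since undiagnosed disease could meet them all. A diluted healing effect has no figure or support in the document.

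**Conclusion.** This is a clerical slip. Section 2.4 states the ratio the opposite way round from every use of the index in the protocol, including the same paragraph, and the sentence should be reconciled with those uses whenever the text is next revised. The literal reading would be serious, admitting all legs with ankle/arm up to 1.25, but nothing in the document leads anyone to apply it. The passages that decide eligibility agree with one another on direction, and the values come from routine records.

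The conclusion assumes that the services calculate the index in the direction in which the protocol interprets it. Section 10.1 supports this by describing the ABI as their routine check before compression. How often anyone would calculate from the written sentence is unknown, and no misclassification rate can be given. That it is the only definition can be said only of the text available; the abbreviations list mentioned in Appendix 4 is not in it. No threshold, sample size, endpoint or analysis depends on the point.
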